8.9 Future Biomedical Research Sample Collection

If the participant provides documented informed consent for future biomedical research, the following specimens will be obtained as part of future biomedical research:

- Leftover DNA for future research
- Leftover RNA from Blood RNA Analyses
- Leftover plasma from Blood for ctDNA analyses
- Leftover main study tumor biopsy

8.10 Health Economics Medical Resource Utilization and Health Economics

Not applicable to this study.

8.11 Visit Requirements

Visit requirements are outlined in Section 1.3, [Table 1](#), [Table 2](#), [Table 3](#), [Table 4](#), and [Table 5](#). Specific procedure-related details are provided in Section 8.

8.11.2 Treatment Period/Vaccination Visit

The overall treatment period duration is 2 years. See Sections 4.1.1 (Arm 1), 4.1.2 (Arm 2 Part I), and 4.1.3 (Arm 2 Part II) for treatment details.

Visit requirements are outlined in the SoA. Specific procedure-related details are provided above in Section 8.

8.11.3 Discontinued Participants Continuing to be Monitored in the Study

The Discontinuation Visit should occur at the time study intervention is discontinued for any reason. Visit requirements are outlined in the SoA. Additional details regarding participant withdrawal and discontinuation are presented in Section 7.

8.11.3.1 Safety Follow-up Visit

All AEs that occur prior to the Discontinuation Visit should be recorded (up to 30 days following end of treatment).

Due to early study discontinuation, participants may be enrolled in a pembrolizumab extension study, if available, to continue pembrolizumab monotherapy. The Safety Follow-up visit will not be required after completion of the Discontinuation Visit.

8.11.3.2 Imaging Follow-up Visits

Due to early study discontinuation, participants may be enrolled in a pembrolizumab extension study, if available, to continue pembrolizumab monotherapy. Imaging Follow-up visits will not be required.

8.11.3.3 Survival Follow-up Contacts

Due to early study discontinuation, participants may be enrolled in a pembrolizumab extension study, if available, to continue pembrolizumab monotherapy. Survival Follow-up contacts will not be required.

9 STATISTICAL ANALYSIS PLAN

This section outlines the statistical analysis strategies and procedures for the primary and secondary analyses of the study. CCI

If, after the study has begun, changes are made to primary and/or secondary objectives, or the statistical methods related to those objectives, then the protocol will be amended (consistent with ICH Guideline E9). CCI

9.1 Statistical Analysis Plan Summary

This section contains a brief summary of statistical analyses for this trial. Full details are in the SAP, Sections 9.2 through 9.12.

Study Design Overview	Phase 1b/2 study of ITu administration of V937 in combination with pembrolizumab in participants with advanced/metastatic solid tumors. Arm 1 (Subcutaneous Tumors) will enroll participants with 3 tumor specific cohorts (Cohort A: TNBC; Cohort B: HNSCC; Cohort C: cSCC). Arm 2 (Visceral Tumors) Part I applies an mTPI design for dose escalation and confirmation of preliminary RP2Ds, followed by Part II expansion phase with 2 tumor-specific cohorts (Cohort D: HCC; Cohort E: Gastric)
------------------------------	---

Intervention Assignment	Participants will be allocated centrally through IRT by nonrandom assignment to receive V937 in combination with pembrolizumab. In Arm 1, participants will be allocated to one of the 3 cohorts (TNBC, HNSCC, cSCC) depending on their tumor types through IWRS. In Arm 2 Part I, participants will be allocated to solid tumors with liver metastases through IWRS. In Arm 2 Part II, participants will be allocated to one of the 2 cohorts (HCC, gastric) depending on their tumor types through IWRS. The trial is open-label.
Analysis Populations	Safety: APaT and DLTe [REDACTED] Efficacy: FAS
Primary Endpoint(s)	Arm 1: 
OR is a confirmed CR or PR by RECIST 1.1 assessed by the investigator Arm 2: 
DLTAEDiscontinuation of study intervention due to AE
Secondary Endpoints	Arm 1: 
AE and discontinuation study intervention due to AEPFS and DOR per RECIST 1.1 assessed by the investigatorOR, PFS, DOR per iRECIST assessed by the investigatorOS Arm 2 Parts I and II: 
OR as evaluated by RECIST 1.1 and iRECIST criteria assessed by the investigator
Statistical Methods for Efficacy/ Immunogenicity/ Pharmacokinetic Analyses	ORR will be estimated using an exact method based on the binomial distribution (Clopper-Pearson interval) together with its 95% confidence interval. [REDACTED]
Statistical Methods for Safety Analyses	Summary statistics (counts, percentages, means, standard deviations, etc.) will be provided for the safety endpoints as appropriate. [REDACTED] [REDACTED] The estimate of the DLT rate among participants treated at RP2D of V937 in combination with pembrolizumab and the 90% Bayesian credible intervals for the estimate will be provided.

CCI	
Sample Size and Power	Arm 1 will enroll 90 participants (30 each for TNBC, HNSCC, and cSCC cohorts) or less due to early study termination. Arm 2 Part I will enroll approximately 35 participants for dose escalation and confirmation, and Arm 2 Part II will enroll 60 participants (30 each for HCC and gastric cohorts) or less due to early study termination. A target sample size of 185 participants will be used for study planning purposes.

9.2 Responsibility for Analyses/In-house Blinding

The statistical analyses of the data obtained from this study will be the responsibility of the Clinical Biostatistics department of the Sponsor.

The study is open-label (ie, participants, investigators, and Sponsor personnel will be aware of participant intervention assignment after each participant is enrolled and treatment is assigned). Participants will be allocated by nonrandom assignment.

9.3 Hypotheses/Estimation

Objectives of the study are outlined in Section 3.

9.4 Analysis Endpoints

9.4.1 Efficacy/Immunogenicity/Pharmacokinetics Endpoints

OR is a confirmed CR or PR based on RECIST 1.1 by the investigator. OR is primary endpoint for the 3 cohorts in Arm 1 and is secondary endpoint for the 2 cohorts in Arm 2 Part II. ORR is the proportion of participants with OR.

[figure not shown]
PFS is defined as the time from the first dose of study treatment to the first documented PD based on RECIST1.1 by the investigator or death due to any cause, whichever occurs first. PFS is secondary endpoint for the 3 cohorts in Arm1.

DOR is defined as the time from the first documented evidence of CR or PR until PD based on RECIST1.1 by the investigator or death due to any cause, whichever occurs first, in participants demonstrating PR or CR. DOR is secondary endpoint for the 3 cohorts in Arm1.

OR, PFS and DOR are also evaluated based on iRECIST by the investigator.

OS is defined as the time from the first dose of study treatment to death due to any cause. Participants who do not die will be censored on the date of the last study assessment or contact. Overall survival is a secondary endpoint for Arm 1.

CCI

9.4.2 Safety Endpoints

The safety endpoints include DLTs, AEs, and discontinuation of study intervention due to AE. In addition, safety and tolerability will be assessed by clinical review of all relevant parameters including SAEs, laboratory tests, and vital signs.

A description of safety measures is provided in Sections 8.3 and 8.4.

9.5 Analysis Populations

9.5.1 Safety Analysis Populations

The APaT population will be used for the analysis of safety data in this study. The APaT population consists of all participants who received at least 1 dose of study intervention.

The DLT evaluable population includes APaT participants that meet the criteria for DLT evaluability (eg, finished Cycle 1 without a DLT or experienced a DLT in Cycle 1). See Section 6.6.5 for details.

At least 1 laboratory or vital sign measurement obtained subsequent to at least 1 dose of study intervention is required for inclusion in the analysis of each specific parameter. To assess change from baseline, a baseline measurement is also required.

CCI

9.5.3 Efficacy Analysis Populations

The FAS population will be used for the analyses of efficacy data in this study. It consists of all participants with a baseline scan that demonstrated measurable disease by the investigator's assessment, and who were administered at least 1 dose of study intervention.

The efficacy analyses for Arm 2 Part II expansion cohort will pool Part I participants who meet the inclusion criteria for the respective Part II tumor type and received the same dose level of V937 in combination with pembrolizumab.

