8.2.3 Tumor Imaging During the Study

Sites will be required to send in anatomical images/medical photography of the needle into lesions during the study drug injection procedures to a central imaging vendor, as indicated in the SIM.

The first on-study imaging assessment should be performed at 9 weeks (63 days \pm 7 days) from the date of first dose (C1D1). Subsequent tumor imaging should be performed every 9 weeks (63 days \pm 7 days) or more frequently if clinically indicated. After 54 weeks, participants who remain on treatment will have imaging performed every 12 weeks (84 days

± 7 days). Imaging timing should follow calendar days and should not be adjusted for delays in cycle starts. Imaging should continue to be performed until disease progression is identified by the investigator, the start of new anticancer treatment, withdrawal of consent, death, or notification by the Sponsor, whichever occurs first.

PR and CR should be confirmed by a repeat imaging assessment. The imaging for confirmation of response may be performed at the earliest 4 weeks after the first indication of response, or at the next scheduled scan (ie, 9 weeks or 12 weeks later), whichever is clinically indicated. Participants will then return to regular scheduled imaging every 9 weeks or 12 weeks, starting with the next scheduled imaging time point. Participants who receive additional imaging for confirmation do not need to undergo the next scheduled tumor imaging if it is less than 4 weeks later; tumor imaging may resume at the subsequent scheduled imaging time point.

Per iRECIST (Section 8.2.5.), disease progression should be confirmed by the site at least 4 to 8 weeks after site-assessed first radiologic evidence of PD in clinically stable participants. Participants who have unconfirmed disease progression may continue on treatment at the discretion of the investigator until progression is confirmed, provided they have met the conditions detailed in Section 8.2.5. Participants who receive confirmatory imaging do not need to undergo the next scheduled tumor imaging if it is less than 4 weeks later; tumor imaging may resume at the subsequent scheduled imaging time point if clinically stable. Participants who have confirmed disease progression by iRECIST as assessed by the site, will discontinue the treatment. Exception is detailed in Section 8.2.5.

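### The visible plan sets no minimum follow-up for the primary ORR, so a sensitivity ORR restricted by first-dose date should be added in case early closure cut off late entrants

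*Combined protocol and SAP*

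**What the plan says.** **Endpoint.** Section 9.4.1: "OR is a confirmed CR or PR based on RECIST 1.1 by the investigator", and "ORR is the proportion of participants with OR". This is primary for the three Arm 1 cohorts and secondary for the two Arm 2 Part II cohorts.

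**Denominator.** Section 9.5.3 defines the FAS as participants with measurable disease on the baseline scan "who were administered at least 1 dose of study intervention". It asks for no post-baseline scan and no minimum time since first dose. Section 9.6.1 reports the ORR by arm and cohort with a Clopper-Pearson 95% CI.

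**Imaging.** Section 8.2.3: "The first on-study imaging assessment should be performed at 9 weeks" (63 days, plus or minus 7), then every 9 weeks, "or more frequently if clinically indicated". On response, "The imaging for confirmation of response may be performed at the earliest 4 weeks after the first indication of response", or it may wait for the next scheduled scan. Imaging can end on notification by the sponsor. Section 8.2.4 requires a scan at discontinuation unless one was taken in the previous 4 weeks.

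**Closure.** The amendment summary says the study is being discontinued by sponsor decision. Sections 4.1.1, 4.1.3 and 9.9 allow cohorts to end below 30. Section 8.11.3.2: "Imaging Follow-up visits will not be required".

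**The concern.** A confirmed response needs two scans separated in time, but the denominator needs only one dose. In a study that runs to plan this matters little, because everyone has either been followed long enough or has failed clinically. Early closure adds a third group: participants whose imaging stops for administrative reasons before a confirmed response could be recorded. Under the FAS and ORR definitions they count in the denominator only.

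Counting early progressors, deaths and clinical drop-outs as non-responders is the usual conservative convention and is not in question. Administrative truncation differs because it reflects calendar date of entry, not treatment effect. Section 2.1 says the combination is to be judged against historical immunotherapy monotherapy, so a cohort ORR lowered by entry timing would be misread. The Clopper-Pearson interval covers sampling error only and would not show it.

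**Working it through.** **1. The plan's own figures.** Exact limits are the Beta(x, n - x + 1) quantile at 0.025 and the Beta(x + 1, n - x) quantile at 0.975. All eight rows of Table 20 (N = 30, 3 to 10 responders) reproduce to one decimal, for example 6/30 = 20.0% (7.7 to 38.6). The total also reproduces: 3 × 30 + 35 + 60 = 185.

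**2. Time needed for a confirmed response** (Section 8.2.3)
- Nominal: 63 + 28 = 91 days = 13 weeks.
- With the scan window: 56 + 28 = 84 days (12 weeks) to 70 + 28 = 98 days (14 weeks).
- Confirmed at the next scheduled scan: 63 + 63 = 126 days = 18 weeks.

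**3. Time needed to complete V937** (Section 4.1.1). Cycle 8 Day 1 falls on day 1 + 28 + 6 × 21 = 155, which is 22 weeks after first dose.

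**4. Size of the effect.** Let m of n participants be cut off before a confirmed response was possible, and f = m/n. Expected ORR = p × (1 - f), where p is the true ORR. This assumes that p does not depend on entry date, that the m participants contribute no responders, and that the others have had time to show their responses. The documents do not give m, so the values below are an assumed range for a cohort of 30. The last two columns show an observed count of responders over 30 - m.

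| m | Expected ORR, p = 20% | Expected ORR, p = 30% | 6 responders over 30 - m | 9 responders over 30 - m |
|---|---|---|---|---|
| 0 | 20.0% | 30.0% | 20.0% (7.7 to 38.6) | 30.0% (14.7 to 49.4) |
| 1 | 19.3% | 29.0% | 20.7% (8.0 to 39.7) | 31.0% (15.3 to 50.8) |
| 3 | 18.0% | 27.0% | 22.2% (8.6 to 42.3) | 33.3% (16.5 to 54.0) |
| 6 | 16.0% | 24.0% | 25.0% (9.8 to 46.7) | 37.5% (18.8 to 59.4) |

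The effect is downward for any m above zero and absent at m = 0.

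**The case against.** The strongest objection is that nothing in the documents shows any participant was first dosed within 13 weeks of the last imaging date. Several provisions point away from an abrupt cut-off. Transfer to the extension study is limited to participants who have completed or discontinued V937, and completers are at about week 22. On-treatment imaging stays in force and a discontinuation scan is still required. Section 8.11.3.2 removes only post-treatment imaging, and the Synopsis and Section 4.1 still describe it. In addition, text is blacked out in 9.1, between 9.5.1 and 9.5.3, in 9.6, and from 9.6.3 into 9.9. Section 9.7, which Section 4.2.1.1 says holds a futility analysis, is not visible, and an sSAP is cited. A cut-off rule could be in any of these.

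Most of this stands, and it rules out three stronger readings that a reader might infer:

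- *That closure does bias the ORR downward.* The documents support only a conditional statement, because f is unknown and may be zero.
- *That late entrants had no chance at all of a response.* The window allows confirmation at 12 weeks, and extra scans are permitted when clinically indicated. What they lack is a scheduled opportunity.
- *That the primary denominator should be replaced.* Changing it after the closure decision, in an open-label study whose sponsor monitors aggregated efficacy data (Section 8.4.6), would be harder to defend than the all-treated rule. Restricting by each participant's own last image would be worse. Imaging stops at progression or death, so early failures would drop out and the ORR would be biased upward.

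Some of the concern survives. Participants who discontinue V937 early can transfer before week 13, and no visible text brings extension-study scans back into this study's ORR. A discontinuation scan can show a first response but cannot confirm it. The visible text gives the sSAP the censoring rules for DOR and PFS and any further subgroup analyses, but does not mention ORR follow-up.

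**Conclusion.** The point holds in conditional form. In the visible text the primary ORR has no follow-up requirement, although a confirmed response takes about 13 weeks on schedule (12 to 14 with the window, 18 at the next scheduled scan). If closure cut off imaging before then for a share f of a cohort, the expected ORR is multiplied by (1 - f). For 3 of 30 that is 10% of the true rate, and for 6 of 30 it is 20%. At a true ORR of 30% these are losses of 3 and 6 percentage points.

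These shifts are small beside the sampling error: the interval for 6/30 spans 38.6 - 7.7 = 30.9 points. The study is estimation only, so no test decision depends on it. Counting the affected participants as non-responders follows from the definitions in 9.4.1 and 9.5.3, but it is not written as a missing-data rule. The conclusion also assumes that the redacted sections and the sSAP contain no follow-up or cut-off rule. The point justifies a supplementary analysis and no change to the primary one.

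**What to change.** Keep the full-FAS ORR as primary. Add to Section 9.6.1 a prespecified sensitivity analysis: ORR with its Clopper-Pearson 95% CI, per cohort, among FAS participants whose first dose was at least 18 weeks (two scheduled scans) before a single fixed study-level imaging cut-off date. State that date in the plan.

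Select only by calendar date of first dose, never by scans obtained or by a participant's own last image, so that early progressors and deaths stay in the denominator. Report the number excluded in each cohort. If it is zero, the two estimates coincide and the question is closed. If the sSAP or a redacted section already contains such a rule, a cross-reference in 9.6.1 is enough.

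The cost is a few sentences and one table with a smaller denominator and a wider CI. Two limits should be noted. The 18-week rule also sets aside participants at 13 to 18 weeks, including any with a response already confirmed. It also guarantees only that a response first seen at week 9 could be confirmed, so later-onset responses may still be missed.

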9.6 Statistical Methods

This section describes the statistical methods that address the primary and secondary objectives. CCI

9.6.1 Statistical Methods for Efficacy Analysis

Objective response rate estimates in each treatment arm and cohort will be reported along with the 95% CI using the Clopper and Pearson method.

If the sample size permits, DOR will be summarized descriptively using Kaplan-Meier medians and quartiles. Only the subset of participants with a confirmed CR or PR will be included in this analysis. For PFS and OS, Kaplan-Meier curves and median estimates from the Kaplan-Meier curves will be provided as appropriate. Censoring rules for DOR and PFS will be provided in sSAP.

9.6.2 Statistical Methods for Safety Analysis

Safety and tolerability will be assessed by clinical review of all relevant parameters including AEs, SAEs, laboratory tests, vital signs, ECG measurements, and physical examinations.

Adverse events will be summarized by counts and frequencies for each dose level and/or cohort. Laboratory tests, vital signs, and other safety endpoints will be summarized as appropriate.

For Arm 2 Part I, CCI

The estimate of the DLT rate among participants treated at the RP2D and the 90% Bayesian credible interval based on a prior distribution of Beta (1,1) for the estimate will be provided.

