Pregnancy test for WOCBP only (urine or serum β -hCG)	X						Perform within 72 h prior to C1D1. Urine pregnancy test to be performed as indicated; if test is positive or cannot be confirmed as negative, a serum pregnancy test is required. Additional pregnancy testing can be conducted if required by local regulations or clinically indicated.

Abbreviations: AE=adverse event; AFP=alpha-fetoprotein; ALT=alanine aminotransferase; aPTT=activated partial thromboplastin time; AST=aspartate aminotransferase; β hCG= β human chorionic gonadotropin; C=cycle; CBC=complete blood count; CT=computed tomography; D=day; ECOG=Eastern Cooperative Oncology Group; F=free; h=hour(s); HbsAg=Hepatitis B surface antigen; HBV=Hepatitis B virus; INR=International Normalized Ratio; iRECIST=modified RECIST 1.1 for immune-based therapeutics; IT=intratumoral; IV=intravenous; MRI=magnetic resonance imaging; PT=prothrombin time; PTT=partial thromboplastin time; RECIST 1.1=Response Evaluation Criteria in Solid Tumors, version 1.1; T3=triiodothyronine; T4=thyroxine; TSH=thyroid-stimulating hormone; WOCBP=women of childbearing potential.

1.3.3 Schedule of Activities for Treatment Phase: Arm 2 Part I - Dose Escalation in Participants with Visceral Tumors

Table 3 Schedule of Activities for Treatment Phase: Arm 2 Part I - Dose Escalation in Participants with Visceral Tumors

Study Period:	Treatment Period				Notes
Treatment Cycle / Visit Title:	Cycle 1 (28 days) Cycles 2-8 (21 days) Cycles ≥ 9 (21 days)				For all cycles: Up to 35 cycles of treatment with pembrolizumab and up to 8 cycles (ie, 9 doses) of treatment with V937.
Treatment Days per Cycle	1	8	1	1	
Scheduling/visit Window (Days)	± 0	± 1	± 5	± 5	
Treatment Assignment	X				Treatment assignment can occur up to 3 days prior to C1D1.
Participant ID Card	X				Participant identification card to be updated with treatment number at the time of treatment allocation.
Pembrolizumab Administration (Q3W)		X	X	X	
Cycle 1, Day 1: Following the C1D1 dosing, participants must remain in the clinic for a minimum of 12 h for observation.
 
Cycle 2 and beyond: Study treatments may be administered up to 5 days before or after the scheduled Day 1.
 
Cycles 2-8: V937 will be administered after a 200 mg dose of pembrolizumab is infused over 30 min.
 
For administration details, see Pharmacy Manual.

V937 Administration	X	X	X		
Clinical Procedures/Assessments					

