4.1.2 Arm 2 Part I: Dose Escalation in Metastatic Visceral Lesion Tumors

In Arm 2 Part I of the study, an mTPI design will be used to identify and confirm the RP2D of V937. Three predetermined dose levels of V937 will be evaluated:

Dose level 1: 3×10^7 (3E7) TCID₅₀

Dose level 2: 1×10^8 (1E8) TCID₅₀

Dose level 3: 3×10^8 (3E8) TCID₅₀

The number of participants enrolled per dose level during dose escalation will be based on the occurrence of DLTs per the mTPI design. The maximum RP2D will be capped at 3E8. The administered dose is dependent on the volume of tumor injected (see [Table 10](#) and [Table 11](#)). V937 will be administered ITu on Days 1 and 8 of Cycle 1 (28 days), then Day 1 of Cycle 2 through Cycle 8, for a maximum of 9 doses. The dose of pembrolizumab will remain constant at 200 mg IV every 21 days for a maximum of 35 treatment cycles (approximately 2 years).

In Arm 2 Part I only, each of the first 3 participants in DL1 will undergo an observation period of 5 days before the next participant is dosed. Subsequent participants in all other dose levels will not undergo a staggered enrollment. Dose-finding and confirmation in Arm 2 Part I will end after 14 participants have been treated at any of the selected doses, per mTPI design. The pool-adjacent violators algorithm will be used to estimate the DLT rates across doses in each treatment arm under the assumption of monotonicity between DLT rates and dose levels [Ji, Y. and Wang, S.-J. 2013]. The dose with an estimated DLT rate closest to 30% may be treated as a preliminary RP2D. The totality of the data will be considered before deciding on the dose to carry forward to Arm 2 Part II.

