4.2.1.2 Safety Endpoints

In Arm 1, safety and tolerability of ITu V937 in combination with pembrolizumab is a secondary objective. In Arm 2, safety and tolerability of ITu V937 in combination with pembrolizumab is a primary objective. The primary safety analysis will be based on participants who experience toxicities as defined by NCI CTCAE v5.0 criteria. Safety will be assessed by quantifying the types and grades of toxicities experienced by participants who have received V937 in combination with pembrolizumab.

For AEs, attribution to drug, time-of-onset, duration of the event, its resolution, and any concomitant medications administered will be recorded. Adverse events that will be analyzed include, but are not limited to, DLTs, AEs, SAEs, fatal AEs, and laboratory changes.

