6.1.1 Pembrolizumab Administration

Participants in Arms 1 and 2 will receive pembrolizumab on Day 8 of Cycle 1 (28-day cycle) and on Day 1 of Cycles 2-35 (21-day cycles). A 200 mg IV dose of pembrolizumab will be infused over 30 minutes. For administration details, see the Pharmacy Manual.

6.1.2 V937 Administration for Arm 1 and Arm 2

When selecting lesions for injection during the pre-treatment period, we recommend designating at least 1 lesion(s) to remain noninjected for the duration of study in order to determine maximal treatment effect (ie, abscopal effect). However, in the event such lesions enlarge and/or all other lesions cannot be injected, then such pre-designated lesions may be injected at a later date.

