6.6.2 Immune-Related Events and Dose Modification (Withhold, Treat, Discontinue)

Dose Modification and Toxicity Management for Immune-related AEs Associated with Pembrolizumab

AEs associated with pembrolizumab exposure may represent an immune-related response. These irAEs may occur shortly after the first dose or several months after the last dose of pembrolizumab treatment and may affect more than one body system simultaneously. Therefore, early recognition and initiation of treatment is critical to reduce complications. Based on existing clinical study data, most irAEs were reversible and could be managed with interruptions of pembrolizumab, administration of corticosteroids and/or other supportive care. For suspected irAEs, ensure adequate evaluation to confirm etiology or exclude other causes. Additional procedures or tests such as bronchoscopy, endoscopy, skin biopsy may be included as part of the evaluation.

Dose Modification and Toxicity Management Guidelines for irAEs associated with pembrolizumab monotherapy, coformulations, or IO combinations are provided in **Table 14**.(See Appendix 7 for country-specific requirements.)

Table 14 Dose Modification and Toxicity Management Guidelines for Immune-related Adverse Events Associated with Pembrolizumab Monotherapy, Coformulations or IO Combinations

General instructions:				
irAEs	Toxicity Grade (CTCAE v5.0)	Action With Pembrolizumab Monotherapy, Coformulations or IO Combinations	Corticosteroid and/or Other Therapies	Monitoring and Follow-up
Pneumonitis	Grade 2	Withhold	
 Administer corticosteroids (initial dose of 1 to 2 mg/kg prednisone or equivalent) followed by taper Add prophylactic antibiotics for opportunistic infections 	
 Monitor participants for signs and symptoms of pneumonitis Evaluate participants with suspected pneumonitis with radiographic imaging and initiate corticosteroid treatment
	Recurrent Grade 2, Grade 3 or 4	Permanently discontinue		

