Adverse events, SAEs, and other reportable safety events will be reported by the participant (or, when appropriate, by a caregiver, surrogate, or the participant's legally authorized representative).

The investigator and any designees are responsible for detecting, documenting, and reporting events that meet the definition of an AE or SAE as well as other reportable safety events. Investigators need to document if an SAE was associated with a medication error, misuse, or abuse. Investigators remain responsible for following up AEs, SAEs, and other reportable safety events for outcome according to Section 8.4.3.

The investigator, who is a qualified physician, will assess events that meet the definition of an AE or SAE as well as other reportable safety events with respect to seriousness, intensity/toxicity and causality.

8.4.1 Time Period and Frequency for Collecting AE, SAE, and Other Reportable Safety Event Information

All AEs, SAEs, and other reportable safety events that occur after the participant provides documented informed consent but before intervention allocation must be reported by the investigator if the participant is receiving placebo run-in or other run-in treatment, if the event cause the participant to be excluded from the study, or is the result of a protocol-specified intervention, including but not limited to washout or discontinuation of usual therapy, diet, or a procedure.

- All AEs from the time of intervention allocation through 30 days following cessation of study intervention must be reported by the investigator.
- All AEs meeting serious criteria, from the time of intervention allocation through 90 days following cessation of study intervention or 30 days following cessation of study intervention if the participant initiates new anticancer therapy, whichever is earlier, must be reported by the investigator.
- All pregnancies and exposure during breastfeeding, from the time of intervention allocation through 120 days following cessation of study intervention, or 30 days following cessation of study intervention if the participant initiates new anticancer therapy must be reported by the investigator.
- Additionally, any SAE brought to the attention of an investigator at any time outside of the time period specified above must be reported immediately to the Sponsor if the event is considered related to study intervention.

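### The visible safety plan gives only crude AE frequencies per dose level and cohort, so differences in time on study, much of it possibly on pembrolizumab alone, can look like differences between V937 doses or cohorts

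*Combined protocol and SAP*

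**What the plan says.** For Arm 2, Section 3 lists three primary endpoints: DLT, AE, and discontinuation of a study intervention because of an AE. Section 4.2.1.2 adds: "The primary safety analysis will be based on participants who experience toxicities as defined by NCI CTCAE v5.0 criteria".

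The analysis method is in SAP Section 9.6.2: "Adverse events will be summarized by counts and frequencies for each dose level and/or cohort". Other safety endpoints are to be summarised as appropriate, and the summary in Section 9.1 mentions counts, percentages and similar statistics. The population is everyone who received at least one dose (Section 9.5.1). Extent of exposure is a separate summary in cycles (Section 9.12) and is not used as a denominator for AEs.

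The two drugs run for different lengths of time. Section 1.3.3, Table 3 allows "Up to 35 cycles of treatment with pembrolizumab and up to 8 cycles (ie, 9 doses) of treatment with V937". AE collection follows the longer one. Section 8.4.1 states: "All AEs from the time of intervention allocation through 30 days following cessation of study intervention must be reported by the investigator", and both drugs are study intervention (Section 6).

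DLT is handled differently. Its window is Cycle 1 (Section 6.6.5), it has its own evaluable population (Section 9.5.1), and its rate at the RP2D is reported with a 90% credible interval (Section 9.6.2).

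**The concern.** The Arm 2 objective is the safety of V937 given with pembrolizumab, and AEs are reported by V937 dose level and cohort. A crude frequency counts a participant with two cycles and one with 35 equally, and it rises with time observed. It also credits to the V937 dose level any AE that starts during pembrolizumab alone. Immune-related events from pembrolizumab "may occur shortly after the first dose or several months after the last dose of pembrolizumab treatment" (Section 6.6.2), so such events are expected.

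Time on study will not be balanced between rows of the table:

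- Each dose level opens only after the previous level has completed its 28-day DLT period and a decision has been made (Section 6.3.1).
- The expansion cohorts were expected to start about 12 to 18 months after dose escalation (Section 4.3.1.1).
- The study is closing early, and participants on pembrolizumab alone may transfer to an extension study (Section 4.4.1).
- V937 may be held while pembrolizumab continues (Sections 6.6 and 6.6.6.1).

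The discontinuation endpoint also changes meaning partway through. After Cycle 8 there is no V937 left to stop, so it can only refer to pembrolizumab.

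At stake is how the AE tables are read. A dose level or cohort with longer follow-up may look more toxic, and a late one safer, for reasons unrelated to V937.

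**Working it through.** **1. Reproduce the plan's own figures.** Inputs for Arm 2 Part I: "V937 will be administered ITu on Days 1 and 8 of Cycle 1 (28 days), then Day 1 of Cycle 2 through Cycle 8" (Section 4.1.2), and "Participants in Arms 1 and 2 will receive pembrolizumab on Day 8 of Cycle 1 (28-day cycle) and on Day 1 of Cycles 2-35" (Section 6.1.1). Later cycles last 21 days.

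- V937 doses: 2 + 7 = 9, as stated.
- Length of 35 cycles: 28 + 34 × 21 = 742 days = 2.03 years, matching the stated approximately 2 years.

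**2. Maximum share of time on pembrolizumab alone.**

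- Cycles 1 to 8: 28 + 7 × 21 = 175 days. Cycles 9 to 35: 742 − 175 = 567 days.
- By cycles: 27/35 = 77.1%. By days: 567/742 = 76.4%.
- Last V937 dose: 28 + 6 × 21 + 1 = Day 155. Last pembrolizumab dose: 28 + 33 × 21 + 1 = Day 722. The AE window ends on Day 722 + 30 = Day 752.
- Share of the AE window after the end of Cycle 8: (752 − 175)/752 = 76.7%.
- Share if 30 days after the last V937 dose count as V937 time: (752 − 185)/752 = 75.4%.

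The range is 75% to 77% for a participant who receives all eight V937 cycles and completes 35 cycles of pembrolizumab.

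**3. Share likely to be realised (assumption).** The documents give no expected treatment duration. Suppose discontinuation is exponential with rate λ = ln 2 / median. The expected pembrolizumab-alone share of participant-time is then 1 − (1 − exp(−175λ)) / (1 − exp(−742λ)).

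| Assumed median time on treatment | Pembrolizumab-alone share |
|---|---|
| 2 months | 14% |
| 3 months | 26% |
| 4 months | 36% |
| 6 months | 48% |
| 12 months | 63% |

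**4. Effect of unequal follow-up on a crude frequency (assumption).** Take an AE type with the same constant rate in everyone, whatever the V937 dose. The crude frequency is 1 − exp(−rate × days/365.25).

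| Rate per year | 90 days | 185 days | 752 days |
|---|---|---|---|
| 0.25 | 6% | 12% | 40% |
| 0.5 | 12% | 22% | 64% |

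The underlying rate is identical along each row, so every difference in a row comes from follow-up alone. The 752-day column marks the upper limit. The contrast between 90 and 185 days needs nobody to stay much beyond the V937 period.

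**The case against.** **The primary safety result and the RP2D are not driven by these tables.** A reader might infer that the whole primary Arm 2 safety result is confounded, and the dose choice with it. The documents do not support that. Escalation follows DLTs. The preliminary RP2D may be the dose whose estimated DLT rate is closest to 30% (Section 4.1.2), and DLTs use a common Cycle 1 window. This stands, and the point is limited to the AE and AE-discontinuation endpoints. Those still matter, because Section 4.1.2 also weighs the totality of the data, Section 4.1 uses all available safety information for the final RP2D, and Cycle 1 covers only two of the nine V937 doses.

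**Three quarters is a maximum.** A reader might infer that most AE data will come from pembrolizumab alone. Part I enrols participants who have progressed on all treatment known to confer benefit (Section 5.1.3), and few may reach Cycle 9. This stands too. Under assumed medians of 2 to 6 months the share is 14% to 48%.

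**Late events should count.** Section 6.6 says that AEs associated with V937 and pembrolizumab may appear several months after the last dose, and Section 4.1 wants late toxicities from Arm 1 considered. The full regimen is also what is being studied. This stands, and it is a reason not to let a table cut off at 30 days after V937 replace the full-period table.

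**Attribution and onset are already recorded** (Section 4.2.1.2). That is true, but no visible analysis uses them. Section 10.3.5 directs that causality should in general be assigned to the combination, so attribution alone separates the agents poorly.

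**Text is redacted.** Sections 9.1 and 9.6.2 have redactions in the safety methods, and a supplemental SAP is mentioned in Sections 9.6.1 and 9.10. What is said here about missing analyses therefore applies to the visible text only. That the table covers the whole collection period is likewise inferred from Sections 8.4.1 and 9.5.1, not stated in 9.6.2.

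**Conclusion.** The concern holds within limits. In the visible plan, the Arm 2 AE and AE-discontinuation endpoints have no period split and no exposure-adjusted rate. Up to 27 of 35 cycles are on pembrolizumab alone, and follow-up will differ between dose levels and cohorts. Crude frequencies will therefore partly reflect time on study.

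The 75% to 77% figure follows from the schedule and assumes full treatment with both drugs. Someone who stops V937 early and stays on pembrolizumab would spend a larger share on pembrolizumab alone. The realised share and the size of any distortion depend on treatment durations that the documents do not give. The crude frequencies of 12% and 22% are an illustration under a constant rate of 0.5 per year, not a forecast.

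The DLT analysis and DLT-based escalation are unaffected. In an estimation study without hypothesis testing or a visible planned safety comparison between cohorts, this is a worthwhile improvement to the tables and does not invalidate the plan.

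**What to change.** In Section 9.6.2, keep the full-period table of counts and frequencies as it is. Beside it, for each dose level and cohort, add:

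- (a) AEs and AE-related discontinuations with onset from the first V937 dose to 30 days after the last V937 dose, with the later pembrolizumab-only period shown separately;
- (b) exposure-adjusted event rates for the full period, as events per participant-time.

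The full-period table should keep its standing, because late events related to V937 are possible and would otherwise appear only in the second period.

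The cost is SAP wording and one extra set of tables from AE onset and dosing dates that are already recorded. Nothing changes in treatment, visits or data collection. Exposure-adjusted rates assume a roughly constant hazard, so (b) should be read together with (a). If the redacted text or the supplemental SAP already contains these summaries, the sponsor need only confirm it.
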